8.2 AE and SAE Reporting on Protocol

8.2.1 Adverse Event Grading

Grade	Description
0	No AE (or within normal limits).
1	Mild; asymptomatic or mild symptoms; clinical or diagnostic observations only; intervention not indicated.
2	Moderate; minimal, local or noninvasive intervention (e.g., packing cautery) indicated; limiting age-appropriate instrumental activities of daily living (ADL).
3	Severe or medically significant but not immediately life-threatening; hospitalization or prolongation of hospitalization indicated; disabling; limiting self-care ADL.
4	Life-threatening consequences; urgent intervention indicated.
5	Death related to AE

8.3 Known AEs List

Known Risks and Side Effects Related to Blinatumomab Include Those Which Are:		
Very Common (In 100 people receiving blinatumomab, more than 10 and up to 100 people may have)	Common (In 100 people receiving blinatumomab, between 1 and 10 people may have)	Uncommon (In 1000 people receiving blinatumomab, between 1 and 10 people may have)

 • Anemia (decreased red blood cells) which may require blood transfusion • Thrombocytopenia (decreased platelets, for clotting blood) • Leukopenia (decreased white blood cells) • Pyrexia (fever) • Infusion related reactions • Weight increased • Hypertension (high blood pressure) • Neutropenia (decreased neutrophils with fever) • Increased hepatic enzymes (in the blood, which may be due to inflammation or damage to liver cells) • Tachycardia (rapid heart rate) • Edema (swelling of hands, legs, ankles, feet, face, or trunk) • Back pain 	
 • Leukopenia, Lymphopenia (decreased types of white blood cells) • Leukocytosis (increased white blood cells) • Lymphadenopathy (swelling in lymph nodes) • Hyperbilirubinemia (high levels of bilirubin in the blood) • Decreased immunoglobulins (in the blood, proteins made by the body's immune system to fight against infections and foreign substances) • Increased alkaline phosphatase (in the blood can be due problems in your liver or in your bones) • Chills • Chest pain • Pain in the arms, legs and hands • Overdose, Accidental overdose • Weight increased • Hypertension (high blood pressure) • Flushing 	
 • Speech disorder • Cytokine storm, is a severe form of cytokine release syndrome which is described under the "Very Common" column. • Pancreatitis, inflammation of the pancreas that can be life-threatening or may even lead to death. Symptoms can include severe and persistent stomach pain, with or without nausea and vomiting. • Leukoencephalopathy, a rare, serious disorder of the white matter in the brain that can lead to severe disability and death and for which there is no known prevention,

Known Risks and Side Effects Related to Blinatumomab Include Those Which Are:			
Very Common (In 100 people receiving blinatumomab, more than 10 and up to 100 people may have)	Common (In 100 people receiving blinatumomab, between 1 and 10 people may have)	Uncommon (In 1000 people receiving blinatumomab, between 1 and 10 people may have)	

 • Bone pain • Headache • Insomnia (difficulty falling and/or staying asleep) • Cough • Rash • Hypotension (low blood pressure) • Infections in the blood including bacteria, fungi, viruses or infections in other organs. Serious infections can happen during and after treatment and can lead to death. Serious infections such as sepsis (infection in the bloodstream), and pneumonia (severe lung infection) have been reported in patients treated with blinatumomab. Your doctor may give you antibiotics to treat the infection or stop your treatment with blinatumomab • Infusion related reactions occur during or after the drug is given through the vein. Symptoms of infusion reaction may include headache, rash, itching, flushing, swelling, shortness of breath, nausea and sometimes vomiting. Severe infusion reactions can cause dizziness, severe skin reactions, 	
 • Dyspnea (difficulty breathing, wheezing or respiratory failure) • Hypersensitivity, allergic reactions to blinatumomab, including hypersensitivity, have been reported. Signs and symptoms of allergic reactions can be very similar to infusion reaction. If you have symptoms of an allergic reaction, you should contact the study doctor or his/her study staff immediately. • Hematophagocytic histiocytosis can occur with cytokine release syndrome, described under the "Very Common" column. It is a life- threatening overactivity of your immune system caused by releasing large amounts of inflammatory cytokines. Your doctor may give you medications such as steroids and/or other medications to prevent or treat cytokine release syndrome. • Tumor lysis syndrome (a group of complications from release of large amounts of potassium, phosphate, and nucleic acid caused by the breakdown of tumor cells after cancer treatment). Tumor lysis syndrome may cause kidney failure, abnormal heart rhythm, and can even lead to death. Patients with moderate kidney failure showed an increased rate of tumor lysis syndrome compared with patients with mild kidney failure or normal kidney function. However, this did not lead to permanent discontinuation of treatment with blinatumomab. Your doctor may give you medicines before your 	treatment, or cure. Symptoms can include difficulty thinking, loss of balance, changes in speech or walking, weakness on one side of your body, or blurred or lost vision.	
 • Capillary leak syndrome (leakage of fluid from small blood vessels into other body spaces that could cause swelling of the trunk, arms and legs)

Known Risks and Side Effects Related to Blinatumomab Include Those Which Are:		
Very Common (In 100 people receiving blinatumomab, more than 10 and up to 100 people may have)	Common (In 100 people receiving blinatumomab, between 1 and 10 people may have)	Uncommon (In 1000 people receiving blinatumomab, between 1 and 10 people may have)

difficulty breathing or swallowing, a decrease in blood pressure, and could be life threatening. Signs and symptoms of infusion reaction can be very similar to cytokine release syndrome.
 
 Cytokine release syndrome is when your body releases substances called cytokines during the blinatumomab infusion. This can cause fever, chills, headache, decreased blood pressure, increased liver enzymes, nausea, and vomiting. Cytokine release syndrome symptoms generally are mild to moderate but occasionally can be serious or life-threatening or may even lead to death. Your doctor may give you medications such as steroids and/or other medications to prevent or treat cytokine release syndrome. 	
treatment to help prevent tumor lysis syndrome.
 
 Nervous system problems such as tremor (shaking), dizziness, seizures, somnolence (changes in alertness), paresthesia (abnormal skin sensation such as burning, prickling, tingling), hypoesthesia (numbness), aphasia (difficulty speaking or slurred speech), cognitive disorder (difficulty understanding words), encephalopathy (loss of consciousness, brain malfunction), memory impairment (memory loss), confusion and/or disorientation, or loss of balance. These nervous system problems can be serious, or life-threatening or may even lead to death. Patients with a medical history of neurologic signs and symptoms had a higher rate of neurologic events (such as tremor, dizziness, confusion, encephalopathy and poor coordination). Your doctor will be closely monitoring you and may give you medications such as steroids and/or other medications to treat nervous system problems or stop your treatment with blinatumomab. 	

8.4 What & When to Report: Adverse events and Serious Adverse Events that meet the below criteria are to be collected. Use the CTCAE (Version 5.0) to code and grade AEs. These AEs are to be documented from the time the patient initiates protocol therapy until the patient meets off study criteria. The time frame for reporting of AEs depends on the grade, expectedness, attribution, and date of event in relation to the date of the patient's first and last protocol treatment dose. **Grade 1 and 2 AEs do not need to be reported.**

Reporting Requirements for AEs that occur between **Blinatumomab Day 1 until ≤ 30 Days post last dose of Blinatumomab OR until patient starts a new, non-protocol therapy** (whichever occurs first):

	Grade 3		Grade 4	Grade 5
	Unexpected	Expected	Unexpected or Expected	Unexpected or Expected
Unrelated, Unlikely	Routine	No report (Exception: Routine Report Grade 3 infection)	Expedited (Exception Grade 4 hematological AEs to be routine reported)	Expedited
Possible, Probable, Definite	Routine	No report (Exception: Routine Report Grade 3 infection)	Expedited (Exception Grade 4 hematological AEs to be routine reported)	Expedited

Reporting Requirements for AEs that occur between **> 30 Days post last dose of Blinatumomab OR occur after the start of a new, non-protocol therapy (whichever occurs first) until patient meets Off Study criteria:**

	Grade 3		Grade 4	Grade 5
	Unexpected	Expected	Unexpected or Expected	Unexpected or Expected
Unrelated, Unlikely	Routine	No report (Exception: Routine Report Grade 3 infection)	Routine*	Routine*
Possible, Probable, Definite	Routine	No report (Exception: Routine Report Grade 3 infection)	Expedited (Exception Grade 4 hematological AEs to be routine reported)	Expedited

* Grade 4 and Grade 5 events that occur > 30 days post last dose of protocol therapy (or after the start of a new non-protocol therapy) and are considered unrelated or unlikely related to protocol therapy only require ROUTINE reporting (i.e. patient has recovered from protocol therapy).

How to Report:

- **Routine Reporting** – Complete the AE CRF and submit according to the schedule in the CRF instructions to [contact].
- **Expedited Reporting** – Complete the SAE CRF and email **within 5 calendar days** to [contact].

Coordinating Site's Responsibilities:

- **Routine Reporting** – To collect all data from participating sites and to submit data into

- OnCore for DSMC review at regular intervals.
- **Expedited Reporting** – To collect all data from participating sites, follow-up with participating sites for additional information as needed, and to submit data into OnCore for DSMC review within 5 calendar days. The coordinating site will submit reports to the CHW IRB according to policy. All participating sites should submit any events to the local IRB per local policy.

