8.6 Time Period and Grade of AE Capture

The period of AE capture will include from the beginning of any study procedures through 30 days following the end of the study treatment OR occur after the start of a new, non-protocol therapy (whichever occurs first) until patient meets Off Study criteria.

The criteria for grading toxicities and criteria for dose modifications will be according to CTCAE (Version 5.0).

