8.7 Monitoring and Recording an Adverse Event

8.7.1 Reporting Source: AEs may be spontaneously reported by the patient and/or in response to an open question from study personnel or revealed by observation, physical examination or other diagnostic procedures.

8.7.2 Prior to the Trial: Planned hospital admissions or surgical procedures for an illness or disease that existed before the patient was enrolled in the trial are not to be considered AEs unless the condition deteriorated in an unexpected manner during the trial (e.g., surgery was performed earlier or later than planned).

8.7.3 Pretreatment Events Following Signed Informed Consent: For serious pretreatment events, the investigator must determine both the intensity of the event and the relationship of the event to study procedures.

8.7.4 Treatment Events: For serious AEs, the investigator must determine both the intensity of the event and the relationship of the event to study drug administration.

8.7.5 Not Serious AEs: For non-serious AEs, the investigator must determine both the intensity of the event and the relationship of the event to study drug administration.

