10.7 Primary Analysis (or Analysis of Primary Endpoints)

10.7.1 Endpoints to be Collected

- FC-MRD: minimal residual disease measured by flow cytometry at the end of each cycle of blinatumomab.
- HTS-MRD: minimal residual disease measured by high throughput sequencing at the end of each cycle of blinatumomab.
- Severe Adverse Events: Grade 3 and 4 adverse events attributed to blinatumomab.
- Toxic death rate: deaths attributed to blinatumomab treatment prior to HCT.

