13.4 Case Report Forms

The principal investigator and/or his/her designee will prepare and maintain adequate and accurate participant case histories with observations and data pertinent to the study. Study-specific Case Report Forms (CRFs) will document safety and treatment outcomes for safety monitoring and data analysis. All study data will be entered into OnCore® via standardized CRFs, in accordance with the study calendar, using single data entry with a secure access account. The Clinical Research Coordinator will complete the CRFs as soon as possible upon completion of the study visit; the investigator will review and approve the completed CRFs.

The information collected on CRFs shall be identical to that appearing in original source documents. Source documents will be found in the patient's medical records maintained by Pediatric CTO personnel. All source documentation should be kept in separate research folders for each patient.

In accordance with federal regulations, the Investigator is responsible for the accuracy and authenticity of all clinical and laboratory data entered onto CRFs. The principal investigator will approve all completed CRFs to attest that the information contained on the CRFs is true and accurate.

All source documentation and data will be available for review/monitoring by the MCWCC DSMC and regulatory agencies.

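### Section 8.4 assigns no report to expected, drug-related Grade 3 events that Section 10.7.1 lists as an endpoint, and its tables do not match Sections 10.7.6, 8.1.4 and 8.10

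*Combined protocol and SAP*

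**What the plan says.** Section 8.4 opens: "Adverse events and Serious Adverse Events that meet the below criteria are to be collected". It adds: "Grade 1 and 2 AEs do not need to be reported". Two tables follow. One covers events up to 30 days after the last dose or until a new non-protocol therapy starts; the other covers later events. Each sorts events by grade, expectedness (at Grade 3) and attribution. In both tables, and in both the unrelated and related rows, the expected Grade 3 cell reads "No report (Exception: Routine Report Grade 3 infection)". A routine report is made as follows: "Complete the AE CRF and submit according to the schedule in the CRF instructions".

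Other sections ask for more:

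- Section 10.7.1, the list of endpoints to collect: "Severe Adverse Events: Grade 3 and 4 adverse events attributed to blinatumomab". No restriction by expectedness is stated.
- Section 10.7.5: AEs and SAEs are all to be listed for each patient and summarized.
- Section 10.7.6: CRS and neurologic events go to the sponsor within 24 hours. No grade is stated, and the reader is sent to 8.4 for instructions.
- Section 8.1.4: SAEs reach the coordinating site within five calendar days.
- Section 8.10, SAE row: the PI/coordinating center and the clinical trials office as soon as possible, the DSMC in 5 days, the IRB in 5 days or with the annual report. No limit by grade or expectedness.

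**The concern.** A safety endpoint can only be summarized from events that reach the database. The class that 8.4 exempts lies at the centre of the 10.7.1 endpoint. Section 8.1.3 judges expectedness largely against the Section 8 toxicity list, and Section 8.3 lists cytopenias, raised liver enzymes, CRS and nervous system problems, the last two including serious forms. Many drug-related Grade 3 events would therefore ordinarily be classed as expected.

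If sites apply the tables as printed, a low Grade 3 count in the final report could mean low toxicity or events that were never entered, and a reader could not tell which. With two sites, each might also resolve the conflict differently. For CRS, neurologic events and SAEs the issue is whether, and how fast, the sponsor and the DSMC hear of an event.

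**Working it through.** The plan states no figure on this point, so the check is mainly a comparison of the text.

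**1. What the tables do.** 2 tables × 2 attribution rows × 4 columns = 16 cells. The no-report entry stands in the expected Grade 3 column of every row, so in 4 of 16 cells. Two of those 4 are for possibly, probably or definitely related events. Grade 3 infections are excepted and reported routinely. Related Grade 4 and 5 events are reported in both windows. The loss at issue is therefore confined to expected, related, non-infectious Grade 3 events.

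**2. Does other text settle collection?**

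- Section 8.6 is headed "Time Period and Grade of AE Capture", but it names a period and a grading scale, not which grades are captured.
- Section 8.7.5: "For non-serious AEs, the investigator must determine both the intensity of the event and the relationship of the event to study drug administration". This requires an assessment but does not say where it is entered.
- Section 13.4 says CRFs "will document safety and treatment outcomes for safety monitoring and data analysis" and that all study data are entered on them, but not which AEs are study data.
- Sections 5.2.1 and 5.4.1 have AEs evaluated weekly, so source records should exist.

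These make capture possible. None says that an event given no report in 8.4 must still go on the AE form.

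**3. CRS and neurologic events.** The shortest timeline in 8.4 is 5 calendar days × 24 = 120 hours, against 24 hours in 10.7.6. Section 8.4 has no 24-hour route, exempts Grades 1 and 2, and gives no report for expected Grade 3.

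The unstated grade scope can be sized from the neurologic rates in footnote 2 to Table 1 (about 65% any grade, about 13% Grade 3 or higher):

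- 35 treated: 35 × 0.65 = 22.75 and 35 × 0.13 = 4.55, so about 23 or about 5 subjects.
- 25 treated: 25 × 0.65 = 16.25 and 25 × 0.13 = 3.25, so about 16 or about 3 subjects.

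These figures size the scope question, not the loss. The 13% includes Grade 4 and 5 events, which 8.4 already reports.

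**4. Would the conflict arise in practice?** Section 1.2 reports three Grade 3 CRS cases among 70 children, 3/70 = 4.3% (printed as 4%). With n subjects, P(at least one) = 1 − (67/70)^n. This gives 0.67 for n = 25 (1.1 expected cases) and 0.78 for n = 35 (1.5 expected cases). Those children had relapsed or refractory disease; this trial's subjects are in remission, so the figures may be too high.

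**5. Seriousness.** The tables have no seriousness criterion, although 8.4 names SAEs in its opening sentence.

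| SAE type | 8.4 | 8.1.4 and 8.10 |
|---|---|---|
| Expected Grade 3, non-infectious | No report | Coordinating site within 5 days, PI as soon as possible, DSMC 5 days |
| Unexpected Grade 3 | Routine | Same |
| Unrelated Grade 4 or 5, late window | Routine, with footnote | Same |

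**The case against.** The strongest reply is that 8.4 governs transmission, not data capture. Section 8.1.8 defines routine reporting as reporting to the coordinating site, the tables are headed as reporting requirements, and 10.7.1, 10.7.5 and 13.4 can be read as collection rules in their own right. The CRF instructions cited in 8.4 and the completion guidelines cited in 12.9 might also settle which AEs are entered. This stands to the extent that the events may be captured anyway. It does not remove the conflict, because 8.4 itself says its criteria decide what is collected.

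Section 10.7.6 can fairly be read as the specific rule that prevails on timing, and a site could comply with both sections. That leaves the grade scope open and the cross-reference leading to instructions that do not fit. Likewise, 8.1.4 sets a five-day SAE rule with no grade limit. It gives sites a route, but one that the tables contradict.

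The DSMC list in 11.1.4 follows 8.4 in naming only unexpected Grade 3 events, so the limit may be deliberate. Narrowing 10.7.1 would then also restore consistency, at the price of dropping these events from the endpoint.

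Three stronger inferences are not supported:

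- A reader might infer that nothing carries these events to a CRF. Section 13.4 puts all study data on CRFs and has them completed after each visit; what is missing is a statement of which AEs count.
- A reader might infer that the AE form is used for routine reports and nothing else. Section 8.4 describes how to make such a report and forbids no other entry.
- A reader might treat the admission prescribed for Grade 2 CRS in 7.1.1 as an SAE that 8.4 suppresses. Section 8.1.7 excludes hospitalization for protocol or standard-of-care treatment, so that case arguably falls outside the SAE definition.

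**Conclusion.** The inconsistency is in the current text and should be fixed. Sites following the 8.4 tables could omit expected, related, non-infectious Grade 3 events from the AE form, and the Grade 3 part of the 10.7.1 endpoint could be undercounted. The size cannot be estimated: the documents give no rate of drug-attributed, expected Grade 3 events for patients in remission. Nor is an undercount certain, since it depends on sites applying the tables literally and on CRF instructions that are not part of these documents.

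The mismatches with 10.7.6 (24 against 120 hours, grade scope unstated) and with 8.1.4 and 8.10 (no seriousness criterion) are plain from the wording.

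The consequences are limited. The endpoint is descriptive and no test or decision rule rests on it. The primary MRD endpoint and the toxic-death rule are unaffected.

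**What to change.** One amendment, mainly to Section 8.4:

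1. In the possible/probable/definite row of both tables, change the expected Grade 3 cell from no report to Routine, so that the 10.7.1 endpoint is collected as stated.
2. Put the 24-hour route for CRS and neurologic events into 8.4, and state the same grade scope, chosen by the sponsor, in 8.4 and 10.7.6.
3. Add to 8.4 that any event meeting 8.1.7 is reported as an SAE under 8.1.4 and 8.10 whatever its grade, expectedness or attribution, overriding the no-report, Routine and footnoted Routine cells and the Grade 1 and 2 sentence. Alternatively, for late unrelated Grade 4 and 5 events, reconcile 8.10 with the footnoted rule. The override would also reach serious Grade 4 hematological events, which 8.4 and 11.1.4 now allow as routine reports; the sponsor should say whether that exception is to survive.

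The cost is a modest number of extra AE form entries for at most 35 subjects over one or two cycles. Section 8.1.5 limits entries to the worst grade of each event per cycle. The number of 24-hour neurologic reports depends on the scope chosen: about 5 to 23 of 35 subjects on the footnote rates. AEs are already evaluated weekly, so no new procedure is needed.

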Of note, most AEs in the psychiatric disorder category are unlikely to be caused by blinatumomab and generally require supportive care rather than dose modification or discontinuation of blinatumomab (e.g., Insomnia, Depression, Anxiety). Psychiatric AEs that may reflect underlying central nervous system toxicity (e.g., Confusion, Delirium, Hallucinations, Psychosis) are of

greater interest, particularly if accompanied by other AEs in the nervous system disorders category" follow the recommendations from the USPI.

3. In the first days of treatment, transient DIC-like pictures may develop. Because patients are at risk for capillary leak syndrome and cytokine release syndrome, appropriate supportive care with dexamethasone (described above), blood products and factors (packed red cells, platelets, cryoprecipitate, fresh frozen plasma), vitamin K, and/or albumin should be considered according to institutional standards of care. Particularly in the first week of infusion, when the risk of capillary leak and cytokine release is more prominent, appropriate use of blood products and factors is preferred if laboratory indications suggest the need for replacement, as large volumes of crystalloid fluids tend to exacerbate the capillary leak.
4. In the first days of treatment, a rapid transient drop in platelets, neutrophils and/or hemoglobin may be observed. These effects are not necessarily cytokine-mediated. Counts typically recover to baseline during treatment, and usually within two weeks of starting blinatumomab. Transfusion of blood and platelets should be performed according to appropriate institutional standards.
5. In the first days of treatment, transient increases in transaminases up to over 1000 U/L may develop. These have generally returned to baseline in the 1st week of treatment.
6. Decrease in serum immunoglobulins have been observed in patients treated with blinatumomab. Intravenous immunoglobulin should be administered according to institutional standards but is recommended for any patient with a total IgG level below 400. Immunoglobulin must not be administered through the line through which blinatumomab is actively being infused.

* Definitions of supportive care abbreviations:

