Hospitalization: An event that results in an admission to the hospital for any length of time. This does not include an emergency room visit or admission to an outpatient facility. Additionally, any hospitalization for the purpose of treatment as per the protocol or any standard of care treatment will not be considered an SAE.

Prolongation of Hospitalization: An event that occurs while the study patient is hospitalized and prolongs the patient's hospital stay.

Congenital Anomaly: An anomaly detected at or after birth, or any anomaly that results in fetal loss.

Persistent or Significant Disability/Incapacity: An event that results in a condition that substantially interferes with the activities of daily living of a study patient. Disability is not intended to include experiences of relatively minor medical significance such as headache, nausea, vomiting, diarrhea, influenza, or accidental trauma (e.g., sprained ankle).

Important Medical Event Requiring Medical or Surgical Intervention to Prevent Serious Outcome: An important medical event that may not be immediately life-threatening or result in death or hospitalization, but based on medical judgment may jeopardize the patient and may require medical or surgical intervention to prevent any of the outcomes listed above (i.e., death of patient, life-threatening, hospitalization, prolongation of hospitalization, congenital anomaly, or persistent or significant disability/incapacity). Examples of such events include allergic bronchospasm requiring intensive treatment in an emergency room or at home, blood dyscrasias or convulsions that do not result in inpatient hospitalization, or the development of drug dependency or drug abuse.

8.1.8 Routine Reporting: AE reporting to the coordinating site at the time of the regularly scheduled time points listed in the Case Report Forms (CRFs).

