9.3 Evaluation of Safety

Analyses will be performed for all patients having received at least one dose of study drug. The study will use the CTCAE (Version 5.0) for reporting of nonhematologic adverse events and modified criteria for hematologic adverse events. See Section 8.

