11.1.4 DSMC

The Pediatric CTO places the highest priority on ensuring the safety of patients participating in clinical trials. Every cancer interventional trial conducted at CHW includes a plan for safety and data monitoring.

More information can be found related to the MCWCC Data and Safety Monitoring Plan at the MCWCC website ([Data and Safety Monitoring Plan](#)).

This study will be reviewed by the Medical College of Wisconsin Cancer Center Data and Safety Monitoring Committee (MCWCC DSMC). A summary of the MCWCC DSMC activities are as follows:

- Review the clinical trial for data integrity and safety
- Review all unexpected Grade 3, and all Grade 4, and 5 adverse events (with the exception of Grade 4 hematological AEs, which can be routine reported), as well as any others requiring expedited reporting as defined in this protocol. (Grades 4 & 5 events must be reported to the DSMC within 5 calendar days of study staff's knowledge.)
- Review all DSM reports
- Submit a summary of any recommendations related to study conduct
- Terminate the study if deemed unsafe for patients

A copy of the MCWCC Data and Safety Monitoring Plan and membership roster will be maintained in the study research file and updated as membership changes. The committee will review reports from the study PI twice annually (or more frequently if needed) and provide recommendations on trial continuation, suspension or termination as necessary.

Any available DSMC letters will be submitted to the IRB of record as required.

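### Sections 8.4 and 11.1.4 let a life-threatening Grade 4 hematologic event go to routine reporting, although 8.1.4, 8.1.7 and 8.10 put any life-threatening SAE on a 5-day clock

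*Combined protocol and SAP*

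**What the plan says.** Section 8.4 covers both AEs and SAEs and has two tables, one for each time window.

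- **Grade 4 cells.** Three of the four carry the exception "Expedited (Exception Grade 4 hematological AEs to be routine reported". In the on-treatment window it stands in both attribution rows, under a column that combines unexpected and expected events. In the later window it stands in the related row. The remaining cell, for later unrelated events, is routine for every Grade 4 event.
- **Forms.** Section 8.4 ties routine reporting to the AE form and expedited reporting to the SAE form, which is due in 5 calendar days.
- **DSMC.** Section 11.1.4 lists Grade 4 events for DSMC review "with the exception of Grade 4 hematological AEs, which can be routine reported".

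Other sections carry no such exception.

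- **8.1.4** defines expedited reporting as sending SAEs to the coordinating site within 5 calendar days.
- **8.1.7** makes an event an SAE if it is life-threatening in the investigator's opinion. Its examples of important medical events include "blood dyscrasias or convulsions that do not result in inpatient hospitalization".
- **8.10** gives every SAE 5 days to reach the DSMC.

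The term hematological is never defined. Section 8.4 says "Use the CTCAE (Version 5.0) to code and grade AEs" but names no category or list of terms. Section 9.3 speaks of "modified criteria for hematologic adverse events" and points to Section 8, which contains none.

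**The concern.** An exemption for low blood counts is sensible. Section 8.3 lists anemia, thrombocytopenia and leukopenia as very common with this drug, and footnote 4 to Table 1 describes an early, transient fall in counts. Expedited reports of each one would swamp the DSMC.

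The wording reaches further than that. Section 8.2.1 describes Grade 4 as "Life-threatening consequences; urgent intervention indicated", and the exception covers events that are unexpected and related to the drug. The protocol also describes blood-related toxicity that is not simply a low count. Footnote 3 to Table 1 says "In the first days of treatment, transient DIC-like pictures may develop". A site could reasonably call a severe event of that kind hematological and follow the table.

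What is at stake is prompt independent review. The numerical toxicity rule in Section 10.4 counts toxic deaths only, so a non-fatal Grade 4 event triggers no boundary.

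**Working it through.** No design figure is involved. The check compares the two reporting routes for one event and then does the arithmetic on their clocks.

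**Test event:** a Grade 4 hematologic event during blinatumomab, unexpected, possibly related, and life-threatening in the investigator's opinion.

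| Step | Route under 8.4 and 11.1.4 | Route under 8.1.4, 8.1.7 and 8.10 |
|---|---|---|
| Classification | Grade 4 hematological, so excepted | Life-threatening, so an SAE |
| Form or route from the site | AE form, on the CRF schedule | SAE report to the coordinating site in 5 calendar days |
| To the DSMC | Entered for review at unspecified regular intervals | 5 days |
| Hematological exception | Yes | None |

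Neither set of sections says which prevails. Section 8.4 cannot be read as covering only non-serious events, because it states that it covers SAEs. Section 11.1.4 is itself unclear: the same bullet grants the exception and then sets 5 calendar days for Grades 4 and 5 without repeating it.

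**Clocks**

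- Inputs: DSMC review twice a year or more often (11.1.4); 5 calendar days for the site and 5 for the coordinating site (8.4); 6 to 8 consents per year (10.3.2).
- Routine route, longest wait: 12 months / 2 reviews = about 6 months. It is shorter if reviews are more frequent. Section 11.1 leaves the report interval open between biannual and monthly.
- SAE route: 5 days, or 5 + 5 = 10 days if the site and coordinating-site steps run one after the other.
- Consents during the longest wait: 6 × 0.5 = 3 to 8 × 0.5 = 4. These are consents, not treatment starts.

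**The case against.** **The SAE rules already cover it.** Section 8.10 has no hematological exception, and the wording in 11.1.4 is permissive. A careful site would report a life-threatening event in 5 days. This stands to the extent that the exception does not abolish the SAE route. It does not settle the matter, because 8.4 also claims SAEs and assigns excepted events to the AE form. The result is a conflict, and sites may resolve it differently.

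**DIC and hemophagocytic events are not classed as hematological.** This is correct. A reader might infer that the tables as written include both, but no section says so, and how CTCAE classes them is not in the documents. For the second, Section 8.3 says "Hematophagocytic histiocytosis can occur with cytokine release syndrome" and describes immune overactivity. Grade 4 CRS has no exception in 8.4, and CRS is also due to the sponsor within 24 hours under 10.7.6. What stands is narrower: the undefined term can be read to include such events, more readily a DIC-like coagulopathy. Section 10.7.6 does not name DIC, and its report goes to the sponsor, not the DSMC.

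**Other safeguards exist.** A reader might infer that prompt DSMC review is the only protection and that the exception removes it. The documents do not support that. Section 11.1.1 provides study-team review of SAEs and of further enrollment, with weekly group meetings. Section 8.10 has IRB reporting and a 5-day DSMC row for unanticipated problems. Table 1 has patient-level rules for Grade 4 events. What can be lost is early independent review.

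**Conclusion.** The point holds as a contradiction between sections together with an undefined term. During treatment, a life-threatening Grade 4 hematologic event is routine under 8.4 and 11.1.4 and a 5-day report under 8.1.4, 8.1.7 and 8.10. A site following the 8.4 tables can delay the DSMC's first sight of it from 5 days to the next periodic review.

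About 6 months is an upper bound. It assumes strictly twice-yearly reviews, an event just after one of them, and no notice by another route.

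The number of subjects affected cannot be estimated. The documents give no rate for Grade 4 DIC or hemophagocytic events. A reader might be tempted to use the frequency band for hemophagocytic histiocytosis in 8.3, but that band is for any grade and comes from a general risk list. Subjects here enter with under 5% blasts, and Section 1.2 says CRS, with which 8.3 associates that event, is more prevalent at higher leukemia burden.

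**What to change.** In the three 8.4 cells that carry the exception, and in 11.1.4, limit it to Grade 4 laboratory cytopenias (hemoglobin, neutrophils, white cells, lymphocytes, platelets) that meet no 8.1.7 SAE criterion in the investigator's judgment. State there that any Grade 4 hematologic event meeting an 8.1.7 criterion, and every other Grade 4 hematologic event, such as DIC or a hemophagocytic event, follows the expedited 5-day path.

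This brings 8.4 and 11.1.4 into line with 8.1.4 and 8.10, so 8.10 needs no new exemption. In the same amendment, either supply the modified hematologic criteria that 9.3 refers to or delete the reference.

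The cost is a wording change in 8.4 and 11.1.4, a small correction around 9.3, and a few extra expedited reports. Endpoints, sample size and treatment rules are unaffected.
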